4.3. End of Study Definition

The end of the study is defined as the date of the last visit of the last participant in the study.

5. STUDY POPULATION

This study can fulfill its objectives only if appropriate participants are enrolled. The following eligibility criteria are designed to select participants for whom participation in the study is considered appropriate. All relevant medical and nonmedical conditions should be taken into consideration when deciding whether a particular participant is suitable for this protocol.

Prospective approval of protocol deviations to recruitment and enrollment criteria, also known as protocol waivers or exemptions, is not permitted.

5.1. Inclusion Criteria for Healthy Participants

Participants are eligible to be included in the study only if all of the following criteria apply:

Age and Sex:

1. Healthy male participants who, at the time of screening, are between the ages of 18 and 55 years, inclusive. Healthy is defined as no clinically relevant abnormalities identified by a detailed medical history, full physical examination, including temperature, BP and pulse rate measurement, pulse oximetry, 12-lead ECG or clinical laboratory tests.

Type of Participant and Disease Characteristics:

2. Participants who are willing and able to comply with all scheduled visits, treatment plan, laboratory tests, and other study procedures.
3. Chest X-ray with no evidence of current, active TB or previous inactive TB, general infections, heart failure, malignancy, or other clinically significant abnormalities taken at Screening or within 3 months prior to Screening and read by a qualified radiologist.
4. Additional criterion for participants to be enrolled in Japanese cohort only: Japanese participants who have four Japanese biologic grandparents born in Japan.

Weight:

5. Body Mass Index (BMI) of 17.5 to 30.5 kg/m² and a total body weight >50 kg such that the calculated total volume of the IV infusion of PF-06755347 will not exceed 1 liter.

Informed Consent

6. Capable of giving signed informed consent as described in [Appendix 1](#), which includes compliance with the requirements and restrictions listed in the informed consent document (ICD) and in this protocol.

5.2. Exclusion Criteria for Healthy Participants

Participants with any of the following characteristics/conditions will not be included in the study:

Medical Conditions

1. Evidence or history of clinically significant hematological, renal, endocrine, pulmonary, gastrointestinal, cardiovascular, hepatic, psychiatric, neurologic, or

allergic disease (but excluding untreated, asymptomatic, seasonal allergies at the time of dosing).

Diagnostic assessments

2. A positive urine drug screen.
3. Participants with a history of autoimmune disorders and other conditions that compromise or impair the immune system (including but not limited to: Crohn's Disease, rheumatoid arthritis, scleroderma, systemic lupus erythematosus, Graves' disease, and asthma) or have a current positive result for the following; rheumatoid factor, anti-nuclear antibody, or abnormal free triiodothyronine (T3), free thyroxine (T4), thyroid stimulating hormone (TSH), or thyroid stimulating antibody (TSAb) suggestive of thyroid disease.
4. Participants with a history of autoimmune deficiency or current evidence of total immunoglobulin G (IgG) or total immunoglobulin A (IgA) deficiency.
5. Participants with a history of migraine.
6. Participants with a history or current evidence from lab safety tests of clinically significant dyslipidemia in the opinion of the investigator.
7. Participants with a history of allergic or anaphylactic reaction to any drug including immunoglobulin.
8. Participants with a fever or skin rash within 7 days prior to dosing.
9. History of active infections within 28 days prior to the screening visit.
10. Participants with a history of or current positive results for any of the following serological tests: Hepatitis B surface antigen (HepBsAg), Hepatitis B core antibody (HepBcAb), Hepatitis C antibody (HCVAb) or HIV.
11. Participants with a history of thromboembolic events.
12. Participants with a history of cyclic neutropenia.
13. History of TB or active, latent or inadequately treated TB infection. All positive TB test result(s) are exclusionary.

Other exclusions

14. History of regular alcohol consumption exceeding 14 drinks/week for male participants (1 drink = 5 ounces [150 mL] of wine or 12 ounces [360 mL] of beer or 1.5 ounces [45 mL] of hard liquor) within 6 months before Screening.

15. Use of tobacco or nicotine containing products in excess of the equivalent of 5 cigarettes per day.
16. Exposure to live vaccines within the 28 days prior to the screening visit.
17. Treatment with an investigational drug within 30 days (or as determined by the local requirement) or 5 half-lives preceding the first dose of investigational product (IP) (whichever is longer). An approved COVID-19 vaccine is considered a concomitant medication. Due to the potential for interference with vaccine efficacy, the last dose of an approved COVID-19 vaccine must be completed 28 days prior to dosing with PF-06755347.
18. Screening supine BP ≥ 140 mm Hg (systolic) or ≥ 90 mm Hg (diastolic), following at least 5 minutes of supine rest. If BP is ≥ 140 mm Hg (systolic) or ≥ 90 mm Hg (diastolic), the BP should be repeated 2 more times and the average of the 3 BP values should be used to determine the participants eligibility.
19. Screening supine 12-lead ECG demonstrating a corrected QT (QTc) interval > 450 msec or a QRS interval > 120 msec. If QTc exceeds 450 msec, or QRS exceeds 120 msec, the ECG should be repeated 2 more times and the average of the 3 QTc or QRS values should be used to determine the participants eligibility.
20. Participants with **ANY** of the following abnormalities in clinical laboratory tests at screening or on admission, as assessed by the study specific laboratory and confirmed by a single repeat tests, if deemed necessary:
 - Aspartate aminotransferase (AST) or alanine aminotransferase (ALT) level $> 1.25 \times$ upper limit of normal (ULN);
 - Total bilirubin level $> 1.0 \times$ ULN; participants with a history of Gilberts syndrome may have direct bilirubin measured and would be eligible for this study provided the direct bilirubin level is \leq ULN;
 - Creatinine levels $> 1.0 \times$ ULN;
 - eGFR of < 90 mL/min/1.73m².
21. Male participants with partners currently pregnant; fertile male participants who are unwilling or unable to use a condom or whose female partners are unable or unwilling to use a highly effective method of contraception as outlined in this protocol for the duration of the study through final study release of the participant (inclusive of final extended immune follow-up visit, if required), or through at least 28 days after the last dose of IP (whichever is longer).
22. Blood donation (excluding plasma donations) of approximately 1 pint (500 mL) or more within 60 days prior to dosing.

23. Unwilling or unable to comply with the criteria in the [Lifestyle Considerations](#) section of this protocol.
24. Participants who are investigator site staff members directly involved in the conduct of the study and their family members, site staff members otherwise supervised by the investigator, or participants who are Pfizer employees, including their family members, directly involved in the conduct of the study.
25. Other acute or chronic medical or psychiatric condition including recent (within the past year) or active suicidal ideation or behavior or laboratory abnormality (including prothrombin time [PT]/international normalized ratio [INR], partial thromboplastin time [PTT], Ddimer, fibrinogen, hematology and ionogram) that may increase the risk associated with study participation or investigational product administration or may interfere with the interpretation of study results and, in the judgment of the investigator, would make the participant inappropriate for entry into this study.

Prior/Concomitant Therapy

26. Use of prescription or nonprescription drugs and dietary supplements within 7 days or 5 half-lives (whichever is longer) prior to the first dose of IP. As an exception, acetaminophen/paracetamol may be used at doses of ≤ 1 g/day. Limited use of nonprescription treatments that are not believed to affect participant safety or the overall results of the study may be permitted on a case-by-case basis following approval by the Sponsor.
27. Herbal supplements must have been discontinued at least 28 days prior to the first dose of investigational product.
28. Due to the potential for interference with vaccine efficacy, the last dose of an approved COVID-19 vaccine must be at least 28 days prior to dosing with PF-06755347.

Prior/Concurrent Clinical Study Experience:

29. Participation in a previous cohort in the current study.

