The benefit/risk analysis for study participants for COVID-19 related illness during the COVID-19 pandemic is similar to the benefit/risk prior to COVID-19. PF-06755347 is proposed to be an immunomodulator similar to IVIg, and so its safety in humans can reasonably be predicted from clinical experience with IVIg. PF-06755347 is not an immunosuppressant that might render an individual more susceptible to the impact of COVID-19. IVIg has been used in COVID-19 infected individuals because of its known immunomodulatory effects and is reported in uncontrolled trials to be helpful in critically ill individuals. There are currently no reports of injury because of the immunomodulatory effects of IVIg in COVID-19 infected individuals.

In contrast, the benefit/risk analysis for study participants who are scheduled to receive or have received a COVID-19 vaccine suggests that appropriate interval between vaccination and administration of PF-06755347 is prudent because of the potential for an immunomodulatory effect to interfere with development of the intended immune response to the vaccine. While this has not been studied for PF-06755347, extrapolation from other immunomodulatory/immunosuppressive agents suggests at least a 28 day interval after completion of the vaccination course should be sufficient to allow a desired immune response.

By the time of discharge after study confinement on Day 8, approximately 3 terminal half-lives of the study drug will have elapsed. Coupled with the rapidity of the cytokine response to study drug, longer duration of confinement for additional observation appears unnecessary. The on-site follow up requirements for the study are standard timelines for participant safety.

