8. STUDY ASSESSMENTS AND PROCEDURES

Participants will be screened within 56 days prior to administration of the investigational product to confirm that they meet the study population criteria for the study. The investigator (or an appropriate delegate at the investigator site) must obtain a signed and dated ICD before performing any study-specific procedures.

A participant who qualified for this protocol but did not enroll from an earlier cohort/group may be used in a subsequent cohort/group without rescreening, provided laboratory results obtained prior to the first dose administration meet eligibility criteria for this study. In addition, other clinical assessments or specimen collections, eg, banked biospecimens, may be used without repeat collection, as appropriate.

Study procedures and their timing are summarized in the [SoA](#). Protocol waivers or exemptions are not allowed.

Immediate safety concerns should be discussed with the Sponsor immediately upon occurrence or awareness to determine if the participant should continue or discontinue study intervention.

Adherence to the study design requirements, including those specified in the [SoA](#), is essential and required for study conduct.

All screening evaluations must be completed and reviewed to confirm that potential participants meet all eligibility criteria. The investigator will maintain a screening log to record details of all participants screened and to confirm eligibility or record reasons for screening failure, as applicable.

Every effort should be made to ensure that protocol-required tests and procedures are completed as described. However, it is anticipated that from time to time there may be circumstances outside the control of the investigator that may make it unfeasible to perform the test. In these cases, the investigator must take all steps necessary to ensure the safety and well-being of the participant. When a protocol-required test cannot be performed, the investigator will document the reason for the missed test and any corrective and preventive actions that he or she has taken to ensure that required processes are adhered to as soon as possible. The study team must be informed of these incidents in a timely manner.

If an IV catheter is utilized for blood sample collections, ECGs and vital sign assessments (pulse rate and BP) should be collected prior to the insertion of the catheter or if not, ensure adequate rest is achieved prior to the collection of vital signs.

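### The 28-day infection and live-vaccine exclusions stop at the screening visit, so up to 56 days before dosing fall outside them

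*Protocol*

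**What the plan says.** Four exclusion criteria use the screening visit as the end of their look-back:

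- Section 5.2 item 9 (healthy participants): "History of active infections within 28 days prior to the screening visit". Section 5.4 item 13 has the same wording for ITP participants.
- Section 5.2 item 16 (healthy participants): "Exposure to live vaccines within the 28 days prior to the screening visit". Section 5.4 item 23 has the same wording for ITP participants.

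Section 8 sets the interval between screening and dosing: "Participants will be screened within 56 days prior to administration of the investigational product". The Schedules of Activities show the screening column as Day -56 to Day -2, with a further inclusion/exclusion check on Day -1.

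Neighbouring criteria count back from dosing instead:

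- COVID-19 vaccine (Section 5.2 item 28): "the last dose of an approved COVID-19 vaccine must be at least 28 days prior to dosing with PF-06755347". Section 5.2 item 17 and Section 5.4 item 24 also count from dosing.
- Herbal supplements (Section 5.2 item 27): "Herbal supplements must have been discontinued at least 28 days prior to the first dose of investigational product".
- Fever or rash (Section 5.2 item 8): "Participants with a fever or skin rash within 7 days prior to dosing". Section 5.4 item 12 matches it.
- Prior ITP therapy (Section 5.4 items 31 to 33).

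**The concern.** An exclusion for recent infection or live vaccination normally serves to keep such events away from the dose. Here the protected period ends at screening, so it moves further from dosing the earlier a participant is screened. The rule can then turn away someone with an older event and admit someone with a more recent one. Section 5 does not permit waivers, so the older exclusion cannot be set aside.

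What is at stake is mainly the reading of safety data. Cytokine release is the main tolerability finding so far. Appendix 10 grades it on fever that has no other explanation. Section 6.6 asks the dose escalation subteam, after a pause, whether IL-6 has come back close to baseline. CRP is in the safety chemistry panel (Appendix 2). An infection or vaccination shortly before dosing could raise any of these and be taken for a drug effect, or raise the baseline and mask one.

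**Working it through.** There is no sample size or error-rate figure to reproduce. The check is date arithmetic.

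**Inputs.** Look-back L = 28 days (Section 5.2 items 9 and 16; Section 5.4 items 13 and 23). Screening takes place S days before dosing, with S from 2 to 56 (Section 8; Schedules of Activities). The fever/rash rule covers the last 7 days (Section 5.2 item 8; Section 5.4 item 12).

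**Formulas.**
- Span covered by the four items: from S + 28 to S days before dosing.
- Days left uncovered up to dosing: S.
- Days covered out of the last 28 before dosing: max(0, 28 - S).
- Days uncovered for febrile or rash illness: max(0, S - 7).

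| S (days before dosing) | Span covered (days before dosing) | Uncovered | Covered of last 28 | Uncovered, febrile or rash illness |
|---|---|---|---|---|
| 56 | 84 to 56 | 56 | 0 | 49 |
| 42 | 70 to 42 | 42 | 0 | 35 |
| 28 | 56 to 28 | 28 | 0 | 21 |
| 14 | 42 to 14 | 14 | 14 | 7 |
| 2 | 30 to 2 | 2 | 26 | 0 |

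For any S of 28 or more, none of the last 28 days before dosing is covered. At S = 56, Day -70 lies inside the covered span (84 to 56) and excludes. Day -20 lies outside it, and outside the 7-day fever/rash rule, and does not.

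**Are long gaps plausible?** Participants are dosed one at a time, at least 120 hours apart for SC dosing (Sections 2.1 and 6.6). An 8-person SC cohort therefore takes at least 7 × 120 / 24 = 35 days from first to last dose. Section 8 also lets someone who qualified for an earlier cohort enter a later one without rescreening. Its condition concerns laboratory results, not infection or vaccine history.

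**What else could catch an event between screening and dosing?**

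| Text | Reach |
|---|---|
| Fever/rash items | Last 7 days; no use for a non-febrile infection without rash, or for a vaccine |
| Section 10.8.1 (Appendix 8) | Active infection only; no look-back; a public-emergency appendix |
| Section 5.2 item 26 (drug use) | 7 days or 5 half-lives; vaccines not named; no equivalent general item for ITP |
| Section 5.2 item 25 and Section 5.4 item 29 | Investigator judgement; no time window |
| Day -1 inclusion/exclusion check | Reapplies the same wording, which still points to the screening visit |
| Section 8.3.1 (AEs from consent) and Section 6.5 (treatments in the 56 days before dosing) | The event may be recorded, but no time-based criterion acts on it |

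None of these closes the interval from about Day -56 to Day -8 for a resolved infection or a live vaccine. The gap is widest for live vaccines in ITP participants, where neither the fever/rash item nor a general drug item applies.

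**The case against.** The strongest defence is that these items were never meant to work alone. Day -1 repeats the eligibility check, history, physical examination, hematology and chemistry, including white cells, CRP and ferritin. Section 5.2 item 25 is aimed at conditions that could disturb interpretation and that, "in the judgment of the investigator, would make the participant inappropriate for entry into this study". If an active infection is found under Section 10.8.1, the participant may be rescreened once it resolves; Section 5.6 then repeats every assessment, so the 28 days restart from the new visit. Appendix 10 asks for infection work-up when fever occurs, the healthy cohorts have blinded placebo, and cytokines are summarised as change from baseline. Pairing a screening-anchored history with a check nearer dosing also appears elsewhere: Section 5.4 item 3 (bleeding before screening) sits beside item 4 (current bleeding).

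Much of this stands, and it lowers the chance that an ill participant is dosed. It does not answer the case of an infection that began and resolved after screening, or of a live vaccine given in that interval. The pairing breaks down for vaccines, which have no check nearer dosing.

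Three stronger readings are tempting, but the documents do not support them:

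- **A contradiction with Section 2.3.** That section says that "at least a 28 day interval after completion of the vaccination course should be sufficient", but it concerns COVID-19 vaccine only, and its stated reason is protecting the vaccine response. It is not a general vaccination rule and does not deal with infection. The protocol gives no purpose for the live-vaccine item.
- **Confounded platelet results in ITP.** Section 5.3 item 2 requires two counts in range, one within about 10 days of dosing and one at admission, and Section 6.6 measures change from the immediate pre-dose count. That largely meets the worry.
- **Any infection before dosing is permitted.** It is only not caught by these four items; the partial safeguards above still apply.

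**Conclusion.** The point holds as a gap in four criteria. The time from screening to dosing is not covered by them: 2 days at the shortest, 56 at the longest, and up to 49 for febrile or rash illness. The 56-day figure is the worst case and needs screening on Day -56. The documents do not give the actual distribution of screening dates or say how often an infection or live vaccination falls in the interval, so no frequency can be stated. They also contain no evidence that an infection resolved weeks earlier changes Day 1 IL-6, CRP or temperature; confounding is a plausible risk, greatest for events nearest dosing.

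The conclusion assumes that the criteria are applied as written, with the screening visit and the Day -1 admission treated as separate events, as the Schedules of Activities show them. It also assumes that the 56-day limit still applies to participants carried over from an earlier cohort. It is a modest defect, worth correcting because the correction is cheap.

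**What to change.** Extend Section 5.2 items 9 and 16 and Section 5.4 items 13 and 23 so that each runs *from 28 days before the screening visit through dosing*. The covered span becomes S + 28 days ending at the dose (30 days when S = 2, 84 when S = 56), and the uncovered interval becomes 0 for every S. State that infection and live-vaccine history since screening is confirmed at the Day -1 inclusion/exclusion check.

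Simply moving the anchor to 28 days before dosing is not recommended, because it would drop cover that the protocol now has. With screening on Day -20, the present rule reaches back to Day -48 and excludes an infection on Day -40; a rule counted only from dosing would admit it.

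The cost is one phrase in four criteria and one question at an existing check, with no added visit or test. A few screened participants will be postponed or replaced after an infection or live vaccine during screening.

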5.3. Inclusion Criteria for Participants with ITP

1. Male and female participants ages 18-55 years at time of ICD signature. Female participants may be of non-childbearing or childbearing potential.
2. Diagnosis of Primary ITP. ITP must be diagnosed in accordance with established guidelines.^{17,18}
 - Persistent (>3 months and ≤ 12 months) OR Chronic (>12 months).

AND

- Platelet count 30-75 x 10⁹/L (inclusive) with criteria achieved on 2 qualifying counts
 - The first platelet count must be taken within approximately 10 days prior to dosing. The second platelet count must be taken at the time of admission.
 - There must be at least 5 days between the 2 platelet counts
- 3. Participants must have received and responded to IVIg or corticosteroids as treatment for ITP (response is defined as achievement of platelet count >50 x 10⁹/L and doubling of platelet count from baseline).
- 4. Willing and able to comply with all scheduled visits, treatment plan, lab tests, lifestyle considerations and other study procedures.
- 5. BMI of 17.5 to 30.5 kg/m² and a total body weight >40 kg (88 lbs).
- 6. Capable of giving informed consent, including compliance with requirements and restrictions in ICD and in the protocol.

5.4. Exclusion Criteria for Participants with ITP

Medical Conditions:

1. Evidence or history of clinically significant hematological (other than ITP), renal, endocrine, metabolic, pulmonary, gastrointestinal, cardiovascular, hepatic, psychiatric, neurologic, or allergic disease (but excluding untreated, asymptomatic, seasonal allergies at the time of dosing).
2. Chest X-ray with evidence of current, active TB, previous inactive TB, general infections, heart failure, malignancy, or other clinically significant abnormalities. Chest x-ray must be taken at Screening or within 3 months prior to Screening and read by a qualified radiologist.
3. Any bleeding event requiring medical evaluation or treatment in the 4 weeks prior to screening.
4. Any current bleeding event that, in the opinion of the investigator, requires treatment.
5. Scheduled or anticipated invasive procedures (eg, surgery, dental procedures) within 28 days following PF-06755347 dosing.
6. Splenectomy within ≤180 days prior to PF-06755347 dosing or splenectomy planned during the period of the study.

Diagnostic Assessments:

7. Positive urine drug test.

8. History of any active autoimmune disorder (other than ITP) or other conditions that may compromise or impair the immune system (including but not limited to: Crohn's Disease, rheumatoid arthritis, scleroderma, systemic lupus erythematosus, Graves' disease, and asthma).
9. Participants with a history or current evidence from lab safety tests of clinically significant dyslipidemia in the opinion of the investigator.
10. History of immune deficiency or current evidence of total IgG or total IgA deficiency.
11. History of allergic or anaphylactic reaction to any drug including immunoglobulin.
12. Fever or skin rash within 7 days prior to dosing.
13. History of active infections within 28 days prior to the screening visit.
14. History of Hepatitis B, Hepatitis C or HIV or current positive results for any of the following serological tests - HBsAg, HBcAb, HCVAb or HIV.
15. History of thromboembolic events. For participants in the Czech Republic, see [Appendix 12: Country Specific Requirements](#).
16. History of cyclic neutropenia.
17. Any evidence of latent or active tuberculosis infection.
18. Hemoglobin <9 g/dL.
19. Positive Direct Coombs test.

Other Exclusions:

20. History of regular alcohol consumption for male participants exceeding 14 drinks/week and for female participants, 7 drinks/week (1 drink = 5 ounces [150 mL] of wine or 12 ounces [360 mL] of beer or 1.5 ounces [45 mL] of hard liquor) within 6 months before Screening.
21. Male participants with partners currently pregnant; fertile male participants who are unwilling or unable to use a condom or whose female partners are unable or unwilling to use a highly effective method of contraception as outlined in this protocol for the duration of the study through final study release of the participant (inclusive of final extended immune follow-up visit, if required), or through at least 28 days after the last dose of study intervention (whichever is longer).
22. Pregnant female participants; breastfeeding female subjects; and female participants of childbearing potential who are unwilling or unable to use a highly effective method of contraception as outlined in this protocol for the duration of the study through final study release of the participant (inclusive of final extended immune follow up visit, if

- required), or through at least 28 days after the last dose of study intervention (whichever is longer).
23. Exposure to live vaccines within the 28 days prior to the screening visit.
 24. Treatment with an investigational drug within 30 days (or as determined by the local requirement) or 5 half-lives preceding the first dose of IP (whichever is longer).
 - a. An approved COVID-19 vaccine is considered as a concomitant medication. Due to the potential for interference with vaccine efficacy the last dose of an approved COVID-19 vaccine must be completed 28 days prior to dosing with PF-06755347.
 25. Screening supine BP ≥ 140 mm Hg (systolic) or ≥ 90 mm Hg (diastolic), following at least 5 minutes of supine rest. If BP is ≥ 140 mm Hg (systolic) or ≥ 90 mm Hg (diastolic), the BP should be repeated 2 more times and the average of the 3 BP values should be used to determine participant eligibility.
 26. Screening supine 12-lead ECG demonstrating a corrected QT (QTc) interval > 450 msec or a QRS interval > 120 msec. If QTc exceeds 450 msec, or QRS exceeds 120 msec, the ECG should be repeated 2 more times and the average of the 3 QTc or QRS values should be used to determine participant eligibility.
 27. **ANY** of the following abnormalities in clinical laboratory tests at screening or on admission, as assessed by the study-specific laboratory and confirmed by a single repeat tests, if deemed necessary:
 - AST or ALT ≥ 1.5 x upper limit of normal); If currently taking eltrombopag, AST or ALT $> 3 \times$ ULN;
 - Total bilirubin ≥ 1.25 x upper limit of normal); If currently taking eltrombopag, total bilirubin level $> 1.5 \times$ ULN (Participants with a history of Gilberts syndrome may have direct bilirubin measured and would be eligible for this study provided the direct bilirubin level is \leq ULN);
 - Serum creatinine > 1.5 x ULN;
 - eGFR < 60 ml/min/1.73m² by CKD-EPI Formula.
 28. Participants who are investigator site staff members directly involved in the conduct of the study and their family members, site staff members otherwise supervised by the investigator, or participants who are Pfizer employees (including their family members) directly involved in the conduct of the study.

29. Other medical or psychiatric condition including recent (within the past year) or active suicidal ideation/behavior or laboratory abnormality that may increase the risk of study participation or, in the investigator's judgment, make the participant inappropriate for the study.

30. Participation in a previous cohort in the current study.

Prior/Concurrent Therapy for ITP:

31. ≤ 28 days prior to PF-06755347 dosing:

- Treatment with IVIg or an anti-Rh D antigen agent (eg, WinRho[®]).
- Treatment with high-dose pulse corticosteroid therapy (eg, dexamethasone 40mg/day for 4 days or methylprednisolone 30 mg/kg/day for 3 days).
- Other Anti-inflammatory Drugs, including NSAIDs for Cox-1 and Cox-2 (eg, Ibuprofen, naproxen, aspirin, diclofenac) or anti-IL-6 agents tocilizumab or siltuximab.

32. Within 3 months prior to PF-06755347 dosing:

- Treatment with cytotoxic agents (eg, cyclophosphamide, vincristine).
- Plasmapheresis.

33. Within 6 months prior to PF-06755347 dosing:

- Treatment with rituximab (or any other anti-CD20 agent).

Concomitant Therapy:

34. If receiving corticosteroids, the dose must be < 1 mg/kg prednisone per day or equivalent, must have been stable or decreasing for ≥ 28 days prior to PF-06755347 dosing and must be expected to remain stable or to decrease for the duration of the study.

35. If receiving any of the medications shown below, the dose must have been stable for ≥ 28 days prior to PF-06755347 dosing and must be expected to remain stable for the duration of the study:

- Avatrombopag, eltrombopag, fostamatinib, or romiplostim.
- Adjunct immunosuppressives cyclosporine, azathioprine, mycophenolate, or 6-mercaptopurine.

